Data monitoring will happen throughout the study. At the outset of the study implementation and at subsequent one to two-month intervals, [name] will conduct project staff meetings in which all study personnel who have contact with participants will discuss the safety and proper treatment of research participants. These meetings will be mandatory. This group will also assess participant recruitment, accrual and retention, data quality and timeliness, participant risk versus benefit, and the development of external conditions that could potentially affect the study. Significant problems or adverse events will be reported immediately to the USC IRB and summarized in a report to an NIA-approved safety officer (as described below). Study procedures that negatively affect participants will be halted if they present an immediate hazard to participants. Other protocol changes will not be made prior to IRB approval. [name] will discuss any issues that were identified as adverse events with research personnel at the subsequent project staff meeting to ensure that everyone is informed about events and potential protocol changes. She will also arrange for trainings as needed. If data and/or safety issues come to the attention of [name] between meetings, she will intercede as described above.

Data will also be monitored by a safety officer who is separate from the study and product development team. This person is a medical doctor, and is required and has been approved by the sponsoring funding agency (NIA). The study team must send compiled adverse event reports on a regular schedule (commensurate with the level of risk determined by the IRB) to this person for review. The team expects that semi-annual reports will be sufficient for this minimal risk study and will propose this to the safety officer upon approval from IRB. [name] will send a data and safety monitoring report to the safety officer upon conclusion of the study.

5.a.vi. Dissemination of findings

Study findings will be disseminated through various avenues. MPI [name] will lead dissemination to the academic community. She, or other members of the research team, will submit abstracts to and attend local, regional, and/or national scientific conferences to present findings in oral and/or poster format. Additionally, she will lead or oversee papers submitted to peer-reviewed scientific journals for publication. Because this funded study is a small business grant, much of the study findings will remain confidential to the business partner. All study findings will be presented in a way that protects the intellectual property belonging to Activ Sitting, Inc. Findings will also be reported in future grant submissions for additional research.

5.b. Instrumentation

Various instrumentation will be used for each stage of the study at different time points. Table 3 indicates at which stage and time point each measurement tool is utilized. Details about the tools are included in the subsequent sections. Information about the other stages of the study have been removed.

Table 3: Measurement tools and timing of implementation for the in-home stage of the study

Instrument	In-home Test
Standardized Questionnaires	
Brief Pain Inventory – Short Form	Pre; Post
Musculoskeletal Stiffness Questionnaire	Pre; Post
Brief Fatigue Inventory	Pre; Post
Physical Activity Scale for the Elderly (PASE)	Pre; Post
Self-efficacy for Exercise	Pre
Study-specific Tools	
Screening, Contact, Referral Form	Pre-consent
Background Questionnaire	Pre
Initial Impression of FitSitt	Post
Self-efficacy for Using FitSitt	Post
Activity Monitor Instructions Log	Throughout
Qualitative Tools	
Interview Guide – In-home	Post
Additional Tools	
activPAL	Throughout
ActiGraph GT9X-BT	Throughout
Notes: Pre = baseline; Pre-consent = prior to consent; Post = after intervention activities; Throughout = utilized/conducted during the entirety of a given session or study period	

5.b.i. Questionnaires/Survey Measures (names and citations)

- Standardized questionnaires
 - Brief Pain Inventory – Short Form (subscale: severity and pain interference): *Pain* will be assessed using two Brief Pain Inventory – Short Form subscales: severity and pain interference. The severity subscale measures amount of pain presently and at its “worst,” “least,” and “average” severity. The interference subscale assesses how much a person’s pain disrupts everyday life. Both subscales are considered valid and reliable (de Andres Ares et al., 2015; Keller et al., 2004; Mendoza et al., 2006). The form takes approximately 5 minutes to complete. For eligibility purposes, if a person marks >8 on question #3, 5, 6, and 9c, these will be treated as red flags that will require follow-up to confirm eligibility.

- Musculoskeletal Stiffness Questionnaire: We will measure *stiffness* using the Musculoskeletal Stiffness Questionnaire (Halls et al., 2016; Watson et al., 2020), a 21-item form that takes ≤ 10 minutes to complete. This patient reported outcome measure has been used to assess overall joint stiffness as well as the physical and psychosocial impact of stiffness on everyday life in healthy adults across the lifespan (Watson et al., 2021). Studies include validation of the tool for persons with rheumatoid arthritis (Halls et al., 2016; Halls et al., 2018) and chikungunya disease (Watson et al., 2020). For eligibility purposes, if a person marks > 8 on question #4 this will be treated as a red flag that will require follow-up to confirm eligibility.
- Brief Fatigue Inventory: *Fatigue* will be measured using the Brief Fatigue Inventory, a 9-item questionnaire that captures subjective report of fatigue severity. It takes approximately 5 minutes to complete. This tool demonstrates good psychometric properties and is sensitive to change (Mendoza et al., 1999). For eligibility purposes, if a person marks > 8 on questions #1, 2, and 4c, these will be treated as red flags that will require follow-up to confirm eligibility.
- Physical Activity Scale for the Elderly (PASE): *Self-reported physical activity* will be measured via the PASE (Washburn et al., 1993). This 10-item instrument assesses physical activity commonly pursued by older adults, including leisure, household, and occupational tasks. The tool is a valid and reliable PA measure in older people (Washburn et al., 1999; Washburn et al., 1993) and takes roughly 5 minutes to complete.
- Study-specific questionnaires
 - Screening, Contact, Referral Form: The screening form includes details for each of the three stages of the study (i.e., focus group, in-lab, in-home) and will be asked based on which stage we are recruiting for at the time. Questions are based on inclusion and exclusion criteria for each study stage. Additionally, important demographic details will be asked (i.e., age, sex, race/ethnicity, TV watching time) for purposes of recruiting a diverse sample of participants as required by the funding sponsors. This screening will be administered as a smart form such that select questions will only arise based on individuals' responses to previous questions and stages of study recruitment. The form includes a section for participant contact information as well as referral source.
 - Background Questionnaire: Basic *demographic*, health-related, health behavior, and technology use data will be gathered using a study-specific questionnaire to characterize the sample. This questionnaire will be administered as a smart form such that questions will branch to additional questions based on responses from the individual. The form is expected to take approximately 5 minutes to complete.
 - Initial Impressions of FitSitt: *Feasibility* and *acceptability* of *FitSitt* will be assessed using a study-specific questionnaire targeting users' cursory impressions of the system. Users are asked a variety of questions targeting issues ranging from perceived ability of the system to meet their health needs to the likelihood the system could be integrated into their daily lives. The form is expected to take approximately 3 minutes to complete.
 - Self-Efficacy for Using FitSitt scale: *FitSitt use self-efficacy* will be assessed using a study-specific adaptation of the Self-Efficacy for Exercise scale (Resnick & Jenkins, 2000). Items have been modified to focus on using *FitSitt* as the mode of SA disruption rather than addressing exercise in general terms. The form is expected to take approximately 3 minutes to complete.
 - Activity Monitor Log: This log was created to assist the research team in data analysis and interpretation of data collected from the activPAL/ActiGraph activity monitors. On this

form the user will document any instances of when the monitors fell or were taken off, wake/bed times, and any other comments they would like to include about monitor wear.

5.b.ii. Qualitative Instruments

- Interview Guide – In-home [embedded in document “Tester Checklist Collect Home bsl” and “Follow-up In-home Interview Guide”]: an audio/video-recorded semi-structured interview, informed in part by the Health Information Technology Usability Evaluation Model (Yen, 2010), will be conducted to evaluate users’ experience, the training, and cursory impressions regarding the system’s feasibility and acceptability. Individuals will be queried about such topics as potential efficacy to impact sedentary activity, physical activity, and health; perceived facilitators/barriers to adopting *FitSitt*; and suggestions for enhancement. Due to the semi-structured nature of the interviews, the interviewer may depart from questions included on the guide in order to probe for pertinent details and follow up on information disclosed by the participants.

5.b.iii. Additional Instruments

- activPAL Activity Monitor: The activPAL (Pal Technologies Ltd) activity monitor—a gold-standard accelerometer device for tracking seated and standing activities in free-living conditions (Grant et al., 2006)—will be placed on the user’s thigh for comparison with data captured with *FitSitt* sensors and through video recording. The monitor is approximately 1.5 square inches and is lightweight. Additional information on the monitor is available here: <https://www.palt.com/>
- ActiGraph GT9X-BT: The ActiGraph GT9X-BT (ActiGraph, LLC) is a research-grade activity tracker within the family of ActiGraph monitoring technology considered to be gold-standard products for real-time assessment of movement. The device can be worn on multiple parts of the body ranging from the wrist to the ankle and has an option for showing activity feedback, which we will not activate for this study’s purposes. Additional information about this device can be found here: <https://theactigraph.com/actigraph-link>. We intend to place the device on the user’s lower body (ankle or attached to their shoe) as we hypothesize this will be the most likely location that will reliably capture the reciprocating movements required during *FitSitt* use.

5.c. Data Analysis

For the focus group, in-lab, and in-home testing phases of the study, procedures primarily include ones that are non-experimental or qualitative in nature, thus non-statistically driven data analyses will be conducted. These results are not reported in the clinicaltrials.gov and thus the analyses are not described here.

The various study stages will also include collection of a background/demographic profile comprised of factors such as *age, sex, race, ethnicity, other demographic characteristics, health-tracking habits, and household income*, and *access to in-home Wi-Fi*. Activity profile data will also be collected using self-report questionnaires addressing *physical activity level* and *self-efficacy to use FitSitt*. Activity and health monitor data (for in-lab and in-home stages) for assessment purposes will come from the research-grade activity monitor (ActivPAL and/or ActiGraph). Health and well-being indices include factors such as *ongoing health problems, health status, BMI (height and weight), pain severity, pain interference, fatigue, and stiffness*. Markers of acceptability of FitSitt are comprised of factors such as *initial impressions of FitSitt*, and address issues such as perceived engagement, and functionality. FitSitt usage data (for in-lab and in-home stages) will be obtained primarily from embedded sensors in the *FitSitt* system. Descriptive statistical analysis on all these variables will be generated for each sample and within key strata such as sex and age group (65–84, 85+) to characterize

the samples.

In-home testing data related to activity, physiological parameters, and *FitSitt* usage patterns will only include activity that takes place during waking hours, as determined by ActivPAL's (and/or ActiGraph's) proprietary algorithm and corroborated by participant activity monitor logs. We will capture and report descriptive statistics on factors such as: *sitting/lying behavior* (total duration sitting/lying per day, mean duration of individual sitting/lying bouts over the day, number of sitting/lying bouts per day, number of sit-to-stand transitions per day), and *activity level* (total sedentary time [ActivPAL/ActiGraph proprietary algorithm], total step counts per day, total stepping time per day). Objective *FitSitt* usage data will be aggregated to produce meaningful summaries of chair usage, such as: *seat occupancy* (total duration sitting in *FitSitt* per day, duration of *FitSitt* sitting bouts per day), *treadle usage* (duration of pedaling bouts per day, frequency of pedaling bouts per day, total time pedaling per day, mean speed during daily pedaling bouts), *synchro-tilt/recline usage* (number of times recliner is engaged per day, mean duration of recliner engagement per day). Additionally, *pain, fatigue, stiffness, and physical activity/sedentary activity behaviors* (self-reported and objective) will be collected both pre-use of the system and at the conclusion of the study. Pre-post scores will be compared, for exploratory purposes, using a paired samples *t*-test (or Wilcoxon signed-rank test) to indicate changes, if any, after having *FitSitt* in the home for a short time. Additionally, we will explore the association of *FitSitt* adherence (minutes of treadle usage dichotomized at the median) to confidence to use *FitSitt* using Spearman correlation. Normalizing transformations will be applied to variables as appropriate; sparse data may be recoded to dichotomous or ordinal data.

Power Analysis

The purpose of this study is to continue *FitSitt* development, and to test the feasibility of study procedures that would be used in a larger study investigating the efficacy of the system to decrease sedentariness in older adults. Accordingly, power calculations are not appropriate. However, sample sizes chosen for each stage of testing are justifiable based on previous research. Iterative product development requires only small samples—5 to 20 users per prototype iteration (Faulkner, 2003)—justifying our modest sample sizes of $N=15-30$. The additional participants beyond the high end of the recommended range will increase chances of identifying lower-level usability issues (Faulkner, 2003; Virzi, 1992). The data from this pilot study will elicit rich information for a properly powered, more in-depth study in Phase II.

References

Atlas, S. J., & Deyo, R. A. (2001). Evaluating and managing acute low back pain in the primary care setting. *Journal of General Internal Medicine*, 16(2), 120-131.

Beck, K. L., Weeks, L. E., Montelpare, W. J., & MacDonald, D. J. (2016). Identifying important factors for older adults' physical activity participation across individual/group, structured/unstructured contexts. *European Journal of Ageing*, 13(3), 209-218. <https://doi.org/10.1007/s10433-016-0376-1>

Berk, D. R., Hubert, H. B., & Fries, J. F. (2006). Associations of changes in exercise level with subsequent disability among seniors: A 16-year longitudinal study. *The Journals of Gerontology Series A: Biological Sciences and Medical Sciences*, 61(1), 97-102. <http://www.ncbi.nlm.nih.gov/pubmed/16456200>

Bertheussen, G. F., Romundstad, P. R., Landmark, T., Kaasa, S., Dale, O., & Helbostad, J. L. (2011). Associations between physical activity and physical and mental health--a HUNT 3 study. *Medicine & Science in Sports & Exercise*, 43(7), 1220-1228. <https://doi.org/10.1249/MSS.0b013e318206c66e>

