It can be easily integrated into older adults' living spaces and everyday routines, maximizing potential for long-term adoption and use. A safe and practical activity-promoting solution for older adults to access in-home, like *FitSitt*, is needed now more than ever in the wake of COVID-19, especially given the pandemic's consequences on people's capacity to lead an active lifestyle (Woods et al., 2020).

2. Purpose/Objectives/Aims/Research Questions

This study had two primary specific aims and associated milestones:

- 1) Build an enhanced *FitSitt* system prototype that includes specialty features and is suitable for user testing.
 - Milestone 1: develop a specifications report for new *FitSitt* features.
 - Milestone 2: build one operational *FitSitt* system compliant with Milestone 1 specifications.
 - Milestone 3: produce the first version (v1) of a Failure Modes Effects and Criticality Analysis (FMECA) report.

- Milestone 4: take corrective actions by reducing critical indices of failure modes to “acceptable” or “consideration” levels or removing them from the system.

2) Assess the initial feasibility, acceptability, and safety of the enhanced *FitSitt* system with target users.

- Milestone 1: collate and categorize available mixed-methods data as process, functionality, hardware, or software information for analysis in a second FMECA cycle.
- Milestone 2: produce a v2 FMECA report that details the necessary corrective actions, and who will take them, to move failure modes into acceptable criticality levels.

The protocol included for clinicaltrials.gov reporting here only contains information relevant to the in-home testing phase of the overall study given this is the only phase that involves a clinical trial.

3. Participants

3.a. Inclusion and exclusion criteria

In-home Testing Stage

Inclusion criteria

- (1) Age 65 years old or older
Justification: the target consumer group for *FitSitt* is older adults.
- (2) English-speaking
Justification: we will not have personnel available for language translation.
- (3) Live in local Los Angeles area and no plans to vacation away from home during the trial period
Justification: research staff will not have the resources to travel outside of the local LA community. Vacation away from home would artificially reduce time spent using the *FitSitt* during the brief trial period.
- (4) Self-reported ability to safely engage in 30 minutes of light-intensity activity per day

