
Recruitment and screening procedures are detailed in section 4.b and 4.d of this document, respectively. Informed consent for the study will take place using the following procedures. If a person fully meets eligibility criteria as determined through screening and continues to express interest in enrollment following screening, an informed consent session will take place either immediately or will be scheduled for a future time, depending on the individual's preference/availability. The consent process will take place either remotely through digital consenting available from REDCap or in person. In all cases, informed consent will be obtained only by authorized, trained study personnel affiliated with USC and not by employees of *Activ Sitting, Inc.* to avoid conflict of interest. Each prospective participant will be given time to read the consent and discuss their options with project staff and family members. To ensure ample time to peruse the consent information, we routinely mail or e-mail copies of a sample informed consent document to each interested party. When the prospective participant is ready, a dialogue regarding the study will ensue. The study team member is responsible for guiding the discussion, and will be instructed to follow a standard format to ensure all required elements are introduced. Explanations will cover all aspects of participation requirements, participants' rights, and other relevant information. Individuals will have an opportunity to ask questions about the study and, if they choose to enroll, will sign a consent form. They will be provided with a copy of the consent form.

Study Procedures: General

This study includes three stages: (1) Focus Group, (2) In-lab Testing, (3) In-home Testing. Study procedures for only the in-home testing phase are delineated below for purposes of clinicaltrials.gov.

Study Procedures: In-home Testing Stage

Overview. A separate set of users ($N=15$) who did not participate in the in-lab activities will complete an in-home trial of a *FitSitt* prototype. The trial period will last between 3 and 7 days (depending on availability of prototypes and scheduling) and will capture free-living feasibility, acceptability, and potential health-relevant short-term benefits of the system. Participation will require two in-person contacts within approximately a 2-week period, which will include pre-session activities, an in-home orientation to *FitSitt*, and a follow-up visit in-home.

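### Safety is an Aim 2 objective, but no listed or described in-home instrument systematically asks about falls, trips or other adverse events, and section 5.c has no adverse-event summary

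*Combined protocol and SAP*

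**What the plan says.** Section 2 makes safety one of three objectives of Aim 2: "Assess the initial feasibility, acceptability, and safety of the enhanced" system. Its first milestone is to "collate and categorize available mixed-methods data as process, functionality, hardware, or software information for analysis in a second FMECA cycle".

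The in-home stage (section 5.a.i) enrols 15 people "who did not participate in the in-lab activities will complete an in-home trial of a" prototype. "The trial period will last between 3 and 7 days", and the overview says that it "will capture free-living feasibility, acceptability, and potential health-relevant short-term benefits of the system". Safety is not named there. The same section anticipates harms: acute soreness from treadle use (Use expectations), and tripping over cords, the foot extension or the tray (Safety considerations and device care).

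Table 3 in section 5.b, headed "Measurement tools and timing of implementation for the in-home stage of the study", contains no adverse-event, fall or injury form. It does schedule pain, stiffness and fatigue questionnaires before and after use. Section 5.b.ii describes the interview as covering experience, training, feasibility, acceptability, possible efficacy, "perceived facilitators/barriers to adopting" the chair, and suggestions. The activity monitor log (5.b.i) covers monitor removal, wake and bed times, and comments on wear.

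Section 5.a.v covers what happens to known events: immediate report to the IRB, review at mandatory staff meetings, and a closing data and safety report. "The study team must send compiled adverse event reports on a regular schedule" to a physician safety officer independent of the study team. Section 5.c specifies descriptive statistics for acceptability, usage, activity and health variables, and exploratory pre-post tests. It names no adverse-event count and no safety variable.

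**The concern.** The plan says where an adverse event goes once staff know of it. It does not say how staff come to know of it, what counts as an event, or how relation to the device is judged. Participants are aged 65 or older and use the chair at home without supervision. A near-fall, a trip on a cord or a sore leg may go unmentioned if nobody asks.

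The v2 FMECA works from whatever data are available, so an event that was never elicited cannot enter it. Phase II would then plan from a record in which few or no events might mean a well-tolerated chair or an unasked question, with no way to tell which. The omission cannot be repaired after the visit.

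**Working it through.** **1. Is harm solicited anywhere in the described text?** Setting the sections side by side:
- Table 3: symptom scales yes; falls, trips, injuries and skin problems no.
- Interview description (5.b.ii): no harm topic named, though the list is given as examples only.
- Activity log (5.b.i): monitor wear only.
- Section 5.a.v: a specific follow-up question is promised about incidents that could produce false usage readings. The protocol thus does describe a solicited question when it wants particular data. It describes none for falls or soreness.

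**2. Is harm analysed?** Section 5.c treats pain, fatigue and stiffness as health and well-being indices and compares them by paired *t*-test or Wilcoxon signed-rank test. A group comparison of this kind can show no change while some participants worsen and others improve. No count of participants who worsened is planned.

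**3. What could 15 participants show with complete ascertainment?** There is no power calculation to reproduce; the Power Analysis section rests N on a usability range of 5 to 20 users per iteration, and 15 lies inside it.
- Upper bound for 0 of 15: 1 − 0.025^(1/15) = 0.218 (two-sided 95%); 1 − 0.05^(1/15) = 0.181 (one-sided 95%).
- Exact (Clopper-Pearson) 95% intervals: 1/15 gives 0.2% to 31.9%; 2/15 gives 1.7% to 40.5%.
- Chance of at least one participant with the event, 1 − (1 − p)^15, over assumed true rates p (the documents give none): 1%, 14.0%; 2%, 26.1%; 5%, 53.7%; 10%, 79.4%; 20%, 96.5%. A 5% event is missed altogether with probability 0.95^15 = 46%.

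**4. What does incomplete ascertainment do?** Let a be the share of affected participants whose event surfaces. The documents give no value, so a is an assumption shown over a range. With p = 10%, the chance of seeing at least one is 1 − (1 − 0.10a)^15:
- a = 1: 79.4%
- a = 0.5: 53.7%
- a = 0.25: 31.6%

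These figures illustrate the direction of the effect; they do not estimate this trial's ascertainment.

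**5. Exposure.** Fifteen participants at 3 to 7 days give 15 × 3 = 45 to 15 × 7 = 105 device-days. Section 4.b calls the in-home period three days, while section 5.a.i gives 3 to 7. The two must be reconciled if exposure is to be reported.

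**The case against.** A reader might infer that no instrument asks about adverse events at all. The documents do not support that. The baseline tester checklist and the follow-up interview guide are cited but not reproduced, the interview topics are open-ended, and the interviewer may probe beyond them. Table 3 is also not exhaustive: the wrist monitor described in section 5.a.i is absent from it. Only *no listed or described instrument* can be said.

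A reader might also infer that the plan yields nothing but spontaneous reports. That goes too far as well. Pain, stiffness and fatigue are solicited pre and post, every participant is due a follow-up interview, and reasons for missing data, including hospitalization and withdrawal, are documented where possible. What remains unsolicited in the described text is mainly falls, near-falls, trips, skin problems and any attribution of symptoms to the device.

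Third, a reader might conclude that the stage can support no safety statement. The aim is *initial* safety, and Aim 2 also has an in-lab stage of 30 participants whose text has been removed, so part of the assessment may lie there. Non-statistical analyses are deliberately left out of this public version. Events that reach staff can be described, and at N = 15 sample size limits any conclusion even with perfect ascertainment.

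These arguments narrow the point without removing it. In-lab data cannot stand in for hazards of free-living use. A safety officer sees only what reaches staff. A count of adverse events is a descriptive statistic, which is what section 5.c sets out for its other variables.

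**Conclusion.** The point holds as a gap in systematic elicitation and in analysis; it is not an absence of safety oversight. Adverse events are reported and reviewed, and three symptom scales are collected. But no described instrument asks every in-home participant about the events that the protocol itself anticipates, and section 5.c summarises neither adverse events nor individual worsening. An absence of reports could therefore not be read as an absence of harm.

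The size of the limitation under the best case is firm: 0 of 15 leaves 21.8% (two-sided 95%) or 18.1% (one-sided 95%), assuming independent participants and complete ascertainment. How much worse incomplete ascertainment makes it depends on a rate that the documents do not give. If the unreproduced guides already contain such questions, the collection part of the point reduces to saying so, and the analysis part remains.

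**What to change.** **Collection.** At the existing follow-up visit, ask every participant a short fixed checklist: fall; near-fall; trip on cord or foot extension; new or worse pain or soreness; skin problem from the monitors; stopped use because of a symptom; and, for each, relation to the device. It can be asked in person or virtually. List it in Table 3. If the interview guide already asks these questions, state that in section 5.b.ii.

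**Analysis.** In section 5.c:
- report each event as n/15 participants with an exact 95% confidence interval;
- give the number whose pain, stiffness or fatigue worsened, by a definition fixed in advance;
- describe total events and total device-days, without an exact per-day interval, because days within one participant are not independent and such an interval would usually be too narrow;
- state that 0/15 would leave an upper bound of 21.8% (two-sided 95%) or 18.1% (one-sided 95%), so the result is descriptive only;
- feed the results into the v2 FMECA.

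**Consistency.** Reconcile the length of the in-home period in section 4.b with that in section 5.a.i.

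**Cost.** A few minutes at a visit that already takes place, and one table. No extra visit or participant is needed. The downside is that more minor events will be recorded and will have to be reported.
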